7.6 Treatment compliance

Patients will be asked about investigational product administration via the mobile application on each treatment day (Day 0 to Day 5).

Vaginal pH assessments on Days 0 and 7 will be used as a measure of investigational product *in vivo* duration. If the vaginal pH on Day 7 is lower than the pH on Day 0, that would indicate appropriate release duration. It will be measured by site personnel on Day 0 and Day 7.

No other measurements of treatment compliance will be made.

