5 STUDY DESIGN

5.1 General outline

This is a multi-centre study to evaluate the clinical performance and safety of treatment with Gedea Pessary in adult women with confirmed VVC.

The study population will consist of post-menarchal, pre-menopausal females, 18 years or older, seeking care for VVC symptoms.

A total of 26 patients are planned to be included in the study.

On Day 0 (Screening, Visit 1), eligible patients will undergo a gynaecological examination, including collection of CVVS data, and vaginal samples. Patients will be provided with 6 doses of Gedea Pessary that will be self-administered as a daily treatment (Days 0 to 5).

Patients will visit the clinic on Day 7 (+2 days, Visit 2) for gynaecological examinations, including collection of CVVS data for the assessment of clinical cure and reporting of AEs and concomitant medications. On Day 14 (± 2 days, Visit 3), patients that did not have a clinical and mycological cure Day 7 will re-visit the clinic for additional gynaecological examinations, including collection of CVVS data for the assessment of clinical cure. Rescue treatment will be offered during visits 2 and 3, if necessary. Patients will have a final telephone follow-up on Day 25 (± 3 days, Visit 4), for reporting of AEs, concomitant medications and potential menstruation onset.

Vaginal sampling for culture and sequencing, as well as vaginal pH measurements will be performed at the clinic on Day 0, Day 7, and Day 14. On Day 25, patients will self-perform vaginal swabs at home for sequencing and vaginal culture.

Patient questionnaires for assessing VVC symptoms, will be used during the treatment period (Days 0 to 5), 1 day after the treatment (Day 6) and on Days 11 and 25. Usability will be assessed on Day 7, also via the patient questionnaire. The patient questionnaire will be based on an electronic patient reported outcomes (ePRO) system, i.e. a mobile application (ViedocMeTM). The questionnaire is provided in Appendix 1.

An overview of the study design is provided in

Figure 1. For details on the specific assessments to be performed at each study visit and contact see [Table 1](#) and [Section 5.4](#).

Figure 1 Study flow chart

[figure not shown]

Table 1 Schedule of assessments and procedures

Evaluations	Day 0	Day 0-5	Day 6	Day 7 (+2 days)	Day 11 (±1 day)	Day 14 ^a (±2 days)	Day 25 (±3 days)
	Screening	Treatment	Follow-up	Follow-up	Follow-up	Follow-up	Follow-up
	Visit 1		At home	Visit 2	At home	Visit 3	Visit 4 (Telephone)

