The diagnosis of VVC in the study is based on the FDA Guidance for Industry. The FDA recommendation is that the patients should have 1) 2 or more of the following signs and symptoms: itching, burning, irritation, edema, erythema, or excoriation; 2) Potassium hydroxide (KOH) or saline preparation from the inflamed vaginal mucosa or secretions demonstrating yeast forms (hyphae or pseudohyphae) or budding yeasts, and 3) vaginal pH ≤ 4.5 . However, in this study, pH ≤ 4.5 will not be an inclusion criterion. The low risk profile of the Gedea Pessary allows this less stringent inclusion criteria and the VVC diagnosis will be confirmed post inclusion, by both vaginal culture and microbiome analysis.

The VVC diagnosis will be validated by culture and microbiome analysis. The vaginal microbiome will be analysed to better understand the relation between vaginal dysbiosis and VVC.

To fulfil the primary endpoint (clinical cure), signs and symptoms of VVC must be absent and this is defined in terms of having a CVVS score ≤ 3 . This is consistent with the current FDA guidelines and the CVVS score is an established method to define VVC signs and symptoms and clinical cure. ⁵³

The safety endpoints were selected to assure a sufficient method to assess the safety of the Gedea Pessary. The usability endpoint was selected to ensure the Gedea Pessary is easy to use for the patients.

The dose of 150 mg GDL and 184 mg NaG administered daily for 6 days was chosen based on clinical data from previous studies (see [Section 3.3.2](#)). Also, pre-clinical measurements of pH in an *in vitro* dissolution test have shown a pH decrease duration of approximately 24 hours for the *p*Hyph gen II (see the IB).

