5.4.2 Day 0 to Day 5; Treatment administration

During Days 0 to 5, patients will self-administer the investigational product, at night before going to bed.

Patients will be reminded about the administration and will also receive questions about VVC symptoms (itching, burning, or irritation) via the mobile application (ViedocMe™) (see [Section 9.1.2](#)).

Procedures to be performed:

- Daily self-administration of treatment (Gedea Pessary) by patients.
- Patient questionnaire (via mobile application)
 - Vulvovaginal symptoms (itching, burning, and irritation), evaluated by patients according to a scoring scale (0-3).

Note that VVC symptoms will also be assessed on Day 6, although no treatment is administered. Additionally, the patient will complete the questionnaire regarding Usability (via mobile application) at Day 6.

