5.4.3 Day 7 (+2 days); Follow-up visit

Patients will visit the clinic on Day 7 to have gynaecological examination performed. The Investigator or an authorised designee will assess the presence of vulvovaginal signs (erythema, oedema, and excoriation) and symptoms (itching, burning, and irritation) and score each sign and symptom on a scale of 0 to 3 (see [Section 9.1.2](#)).

Vaginal samples will be examined under a microscope for yeast forms (hyphae or pseudohyphae) or budding yeast. Vaginal secretion samples collected by swabs will be used for culture and for sequencing analysis of the vaginal microbiome (this sample will be taken in duplicates). If the patient is menstruating at this timepoint, the visit should be postponed until the menstruation is over, even though the visit will happen outside the visit window.

Procedures to be performed:

- Gynaecological examination by Investigator or authorised designee, evaluating vulvovaginal signs (erythema, oedema, and excoriation) and symptoms (itching, burning, and irritation) according to the scoring scale (0 to 3).
- Fungal saline microscopy assessment
- Vaginal swab for
 - Culture
 - Sequencing
- Vaginal self-swab for:
 - Sequencing
- Vaginal pH
- Recording of
 - Concomitant medications
 - AEs
 - Potential menstruation onset
- Product accountability – patients should be asked to return all used and not used treatment packages

Rescue treatment, according to standard clinical practice, will be offered if the intensity of the VVC symptoms is the same or higher compared to the inclusion visit (Visit 1, Day 0). See details in [Section 7.5.2](#).

An assessment of mycological cure will be done as soon as the results from the laboratory are received. A mycological cure is defined as no presence of *Candida* species. If the patient has both a clinical and mycological cure at Day 7, the Day 14 visit should be cancelled.

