7.2.5 Doses and treatment regimens

Each patient will self-administer a total of 6 doses of Gedea Pessary in the study. The pessary is slow-release formulated, administering 150 mg GDL and 184 mg NaG, over 24 hours.

The pessary will be self-administered vaginally by the patient at night, before going to bed. Instructions for use will be distributed at the first visit, advising patients on how to use the product together with the applicator. The patients will also be trained by site personnel in how to use the product, no previous experience of use is needed.

Briefly, patients will be instructed to wash their hands and vaginal area prior to use; place a tablet into the applicator and insert as far into the vagina as is comfortable (without forcing), or until half of the applicator is inside; discard the applicator after use; not use tampons or other vaginal products while using this product.

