10.1.2 Vaginal pH

Patients' vaginal pH will be assessed on Day 0 and on Day 7 by the Investigator or delegatee using a pH-test strip.

Vaginal pH will be used for assessments of investigational product *in vivo* duration. If the vaginal pH on Day 7 is lower than the pH on Day 0, that would indicate appropriate release duration.

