7.9.5 Exploratory endpoints

The endpoint

- Correlation between bacterial vaginal microbiome as assessed by vaginal swab DNA-analysis on Days 0, 7, 14, and 25 and clinical cure.

will not be analysed by CTC. Hence, it is not elaborated on further in this SAP.

The endpoint

- Correlation of presence of fungus as analysed by vaginal swab DNA-analysis on Days 0, 7, 14 and 25 and presence of fungus as assessed by culture

will be addressed descriptively in a frequency table by timepoint. Results will be presented for each fungus species and overall, for any fungus in culture or swab DNA-analysis respectively.

In addition, to assess magnitude of shifts over time the value of fungus as analysed by vaginal swab DNA-analysis will be summarised per timepoint stratified by the magnitude of fungus as assessed in culture, with the latter being expressed as weak, moderate or abundant growth. Results will be presented for each fungus species. The endpoints

- Correlation of presence of fungus as analysed by vaginal swab DNA-analysis on Days 0, 7, 14 and 25 and clinical cure.
- Correlation of presence of fungus as assessed by culture on Days 0, 7, 14 and 25 and clinical cure.

will be addressed descriptively by frequency tables by timepoint. In addition, the magnitude (value) of fungus as analysed by vaginal swab DNA-analysis will be summarized descriptively per timepoint stratified by clinical cure. Furthermore, the relationship between magnitude (value) of each fungus species analysed in culture, and expressed as weak, moderate or abundant, and clinical cure will be summarised descriptively in a frequency table.

Statistical Analysis Plan

Study ID: CL4

Additionally, number of previous infections (0-1, 2 or 3) will be correlated to levels of fungus as analysed by vaginal swab DNA-analysis by summarizing the latter descriptively per timepoint stratified by previous infections.

Change in vaginal pH will be presented with descriptive statistics overall and separately for clinically cured and not clinically cured patients. A decrease from baseline in vaginal pH will indicate appropriate release duration.

All analyses described in this section involving clinical cure will be done for clinical cure as defined in the primary endpoint, i.e. over the period Day 7-14, as well as for clinical cure at Day 7 and 14 respectively.

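### The documents' own 24-hour figures do not support reading a Day 7 fall in vaginal pH as evidence of adequate release duration

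*Protocol*

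**What the plan says.** **The rule.** Protocol 7.6 uses vaginal pH to judge how long the product acts in vivo: "If the vaginal pH on Day 7 is lower than the pH on Day 0, that would indicate appropriate release duration". Protocol 10.1.2 and SAP 6.7 repeat this. SAP 3.3 adds a matching objective, and SAP 3.3.1 (item 5) and 7.9.5 make the pH change an exploratory endpoint, shown overall and by cure status, with the interpretation fixed in advance: "A decrease from baseline in vaginal pH will indicate appropriate release duration". SAP 7.10.1 records that the protocol had not defined pH as an endpoint.

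**The dosing and release figures.** Protocol 5.4.2: "During Days 0 to 5, patients will self-administer the investigational product, at night before going to bed". Protocol 7.2.5: "The pessary is slow-release formulated, administering 150 mg GDL and 184 mg NaG, over 24 hours". Protocol 5.2 says that in vitro dissolution measurements "have shown a pH decrease duration of approximately 24 hours for the" second-generation product, and refers to the Investigator's Brochure.

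**The reading.** Protocol 10.1.2: "Patients' vaginal pH will be assessed on Day 0 and on Day 7 by the Investigator or delegatee using a pH-test strip". The window opens only forwards (Protocol 5.1): "Patients will visit the clinic on Day 7 (+2 days, Visit 2) for gynaecological examinations". For a patient who is menstruating, Protocol 5.4.3 says that "the visit should be postponed until the menstruation is over, even though the visit will happen outside the visit window".

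**The concern.** A measure of release duration should be taken when correct release and short release would look different. Here both are expected to have ended before the pH strip is used. On the stated figures, a pessary that works exactly as described need no longer be lowering pH at the visit, and neither would one that stopped early.

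A fall that is seen at the visit has other possible sources. Protocol 3.1 attributes the weakly acidic vaginal environment to lactic-acid-producing bacteria. Protocol 3.2.2 reports preliminary data in which women cured on the first-generation product had more *L. crispatus*, and uncured women did not. If cured women have lower pH because their flora recovered, the rule would credit that to release. There is no control arm to separate the two.

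At stake is a conclusion in the clinical investigation report. Protocol 5.2 explains the 41% cure rate in CL1 partly by pessaries that dissolved poorly or fell out, and cites smaller pH falls in uncured women as a sign of this. A table of pH change by cure status, read by the fixed rule, could appear to confirm that explanation without testing it.

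**Working it through.** **The plan's own figure.** The 24 hours for the pH effect is an in vitro result held in the Investigator's Brochure. It cannot be reproduced from these documents and is taken as stated.

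**Bound from calendar days alone.** If the last pessary is inserted before midnight on Day 5 and pH is read at any time on Day 7, the whole of Day 6 lies between them. The gap exceeds 24 h without any assumption on clock times.

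**Range with assumed clock times.** Neither document gives a time for the last dose or for the visit. Assumptions:
- Bedtime from 20:00 to 04:00. The 04:00 end is an extreme, borrowed from SAP 6.5, which assigns questionnaire forms started between midnight and 04:00 to the previous study day.
- Clinic visit from 08:00 to 17:00.

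Gap in hours = (visit day − 5) × 24 + visit time − dose time, with a dose after midnight counted as 24 plus the hour (04:00 = 28).

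| Reading on | Shortest gap (04:00 dose, 08:00 visit) | Longest gap (20:00 dose, 17:00 visit) |
|---|---|---|
| Day 7 | 48 + 8 − 28 = 28 h | 48 + 17 − 20 = 45 h |
| Day 8 | 72 + 8 − 28 = 52 h | 72 + 17 − 20 = 69 h |
| Day 9 | 96 + 8 − 28 = 76 h | 96 + 17 − 20 = 93 h |

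More ordinary Day 7 cases lie inside this range: a 22:00 dose and an 08:00 visit give 48 + 8 − 22 = 34 h, and a midnight dose gives 48 + 8 − 24 = 32 h.

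Subtracting the stated 24 h, the reading comes 28 − 24 = 4 h to 45 − 24 = 21 h after the effect should have ended on Day 7, and up to 93 − 24 = 69 h after on Day 9. A visit postponed for menstruation is later still.

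SAP 7.1.2 sets 18:00 on the screening day as the start of the treatment period. That is a convention for defining baseline, not a dosing time. Used as one, it lengthens the gap: 48 + 8 − 18 = 38 h to 48 + 17 − 18 = 47 h on Day 7, and up to 96 + 17 − 18 = 95 h on Day 9.

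**What the reading can show.**
- *Sensitivity.* If the in vivo effect lasts about 24 h, correct release and short release both predict no remaining product effect at the visit.
- *Specificity.* A fall at the visit fits a lasting product effect, and it also fits recovery of the flora after cure. Splitting by cure status shows whether pH change goes with cure, not why.
- *Comparability.* Time since the last dose can differ by about two days between patients within the window, and the analysis does not record or use it.

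**Reach.** The SAP analyses pH descriptively, with no test (7.9.5). It does not enter the primary endpoint (Protocol 12.4.2, SAP 7.9.2), the sample size (Protocol 12.6, SAP 5.1) or the compliance calculation, which uses self-report and returned kits (SAP 8.3).

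**The case against.** The strongest defence is that the 24 hours is approximate and in vitro, while the strip is meant to assess duration in vivo. The release time is not the time for vaginal pH to return to baseline, and no figure is given for the position after six consecutive daily doses. A product-caused fall still present on Day 7 would be compatible with at least 24 h of action. This stands as far as it goes. A reader might infer that the rule is simply invalid, and the documents do not support that. They do leave the rule unjustified, because neither gives in vivo persistence data or a way to attribute a fall to the product.

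A reader might also infer that the plan will label correct release as failed. It does not say so. The rule runs in one direction: a fall indicates adequate duration, and nothing is stated about the absence of a fall. The reverse reading appears in Protocol 5.2, but only for the first-generation product in CL1.

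The flora explanation is plausible, not demonstrated. The data behind it are preliminary, come from the earlier product and report no pH.

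Nor does the trial's rationale depend on Day 7 pH. Retention and loss of the pessary are asked about directly in the usability questions (Protocol Appendix 1, SAP 6.5.2), and device deficiencies are collected under Protocol 10.3.

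**Conclusion.** The point holds in a limited form. If the last dose is taken on Day 5 as scheduled, the pH reading always comes after the 24 h that the documents give for release and for the in vitro pH effect: about 28 to 45 h after the last dose on Day 7, and up to about 93 h on Day 9. These hours rest on the assumed bedtimes and visit times. A reader might take a single figure such as 34 h as the minimum, but the documents fix no minimum in hours. Only the ordering, later than 24 h, is firm, and for a dose before midnight it follows from the calendar alone.

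The stated inference is therefore not supported by the plan's own figures: the reading is insensitive to correct 24-hour release and not specific to release. The consequence is confined to one descriptive exploratory endpoint and its objective. It is worth correcting because the interpretation is fixed in advance and the correction is cheap.

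**What to change.** Remove the release-duration inference from Protocol 7.6 and 10.1.2 and from SAP 3.3, 3.3.1, 6.7 and 7.9.5, and reword the SAP 3.3 objective to match. Alternatively, keep it only if in vivo data are cited showing that the product's pH effect lasts until the time of the visit. If the protocol is no longer open to amendment, record the change in SAP 7.10 and in the clinical investigation report.

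Report the Day 0 to Day 7 change descriptively as post-treatment vaginal pH, overall and by cure status as already planned. Show beside it the number of days from the last pessary reported in the patient questionnaire to the reading. Days are the finest unit available, because the questionnaire asks only whether the pessary was applied on each treatment day and specifies no time of application.

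The cost is wording plus one variable derived from data already collected. Dosing, visits and data collection do not change. The sponsor gives up an exploratory claim about release duration.

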8 ASSESSMENTS

The assessments performed during the study are described in the subsections below.

For details on clinical performance assessments (gynaecological examination and patient questionnaire), see [Section 9](#). For details on safety assessments (clinical laboratory assessments, AEs and device deficiencies), see [Section 10](#).

8.1 Informed consent

The procedures used for screening and obtaining informed consent at Day 0 are described in [Section 6.1](#).

8.2 Demography

Demographic information will be collected at Screening (Day 0) and will include initials, sex, birth date and ethnic origin (Caucasian, Asian or Pacific Islander, African descent, Mixed/multi-racial, or other).

Full information about the patients' Social Security Number or similar and name is to remain confidential in the records of the respective Investigator.

8.3 Eligibility criteria

Eligibility criteria should be checked during Screening (Day 0) and verified before enrollment. The criteria are specified in [Sections 6.3](#) and [6.4](#).

8.4 Prior and concomitant medications

Information about any concomitant medication, including OTC medications and vitamins used by patients within 14 days prior to inclusion and during the study, shall be collected at all site visits (Day 0 and Day 14) for all patients and also at the telephone contacts (Day 7 and Day 25). The generic name or trade name, dosage and reason for use shall be recorded in the eCRF for all medications.

NOTE:

VVC-treatment or any anti-fungal therapy unrelated to VVC within 14 days prior to inclusion, is not allowed (see [Section 6.4](#)).

During the study, anti-fungal therapy and other treatments related to VVC should be avoided (unless rescue treatment at Day 14) (see [Section 6.5](#)).

See further information on rescue medication in [Section 7.5.2](#).

8.5 Medical and surgical history

Medical and surgical history will be collected during the Screening visit (Day 0). It should be obtained by interview and include descriptions of all relevant medical conditions and procedures within 14 days prior to Screening, as judged by the Investigator.

The number of previous VVC infections during the last 12 months prior to inclusion, should be noted, according to exclusion criterion #8 (see [Section 6.4](#)).

Relevant pre-treatment events (pre-treatment AEs) occurring between the signing of ICF and first administration of the investigational product will be registered in the medical history log of the eCRF.

8.6 Pregnancy test

All study patients will perform a pregnancy test (urine dipstick) at Screening (Day 0).

Pregnancy is an exclusion criterion (see [Section 6.4](#)). If pregnancy is confirmed in a patient during the study, the patient will be withdrawn, and the pregnancy will be followed (see [Section 10.4](#)).

8.7 Menstruation

The Investigator or delegatee will ask about onset and end of last menstruation on the Day 0 visit, and ask for possible menstruation onset on Day 7, Day 14 the Day 25. Intermittent bleeding should also be possible to register in the eCRF as AE.

8.8 Administration of investigational product

For details on the administration procedures, see [Section 7.2.5](#).

For restrictions during the treatment period, see [Section 6.5](#).

9 CLINICAL PERFORMANCE

9.1 Clinical performance assessments

Assessments described in [Section 9.1.1](#) will be used to diagnose VVC.

A CVVS score will be used for assessment of the primary endpoint, clinical cure on Day 7-14 (see [Section 4.1.1](#)).

Further, the CVVS score will also be used for assessment of the secondary endpoints 2, 3 and 6 (see [Section 4.2.1](#)).

Assessments described in [Section 9.1.2](#), patient questionnaire, will be used to assess the secondary endpoints 4 and 10 (see [Section 4.2.1](#)).

9.1.1 Gynaecological examination

Patients will undergo a gynaecological examination by the Investigator or an authorised designee at the site visits (on Day 0, Day 7 and Day 14), in order to assess:

- **Vulvovaginal symptoms (assessed by the patient):** Vulvovaginal symptoms (itching, burning, and irritation) will be assessed by patients themselves according to a scoring scale (0-3) as per the patient questionnaire, on Days 0 to 6, Day 11 and Day 25 (see [Section 9.1.2](#)).
- **VVC diagnosis (assessed by the Investigator or designee):** The diagnosis is based on CVVS score and microscopic analysis of a KOH or saline preparation, during the site visits (Day 0, Day 7 and Day 14). The assessments will be recorded in the eCRF. The diagnosis criteria are the following.
 - Having a white or creamy vaginal discharge
 - *At least* 2 of the following signs and symptoms of VVC that are characterised as *at least* moderate^a: itching, burning, irritation, oedema, erythema, or excoriation.
 - KOH or saline preparation from the inflamed vaginal mucosa or secretions revealing yeast forms (hyphae or pseudohyphae) or budding yeasts.

For definition of clinical cure [Section 4.1.1](#).

